4.2.5.1 Adverse events

Summaries of AEs will primarily be based on the on-treatment period, except for fractures and amputations as described in section 4.2.5

In addition to SAEs, the collection of AEs that are not serious is limited to DAEs, AEs leading to interruption of IP or dose reduction and AEs of interest. Thus, summaries of AEs will be limited to these categories and general summaries of all AEs are not planned.

AEs will be classified according to MedDRA by the medical coding team at AstraZeneca data management centre, using the most current version of MedDRA possible.

Summaries by system organ class (SOC) and preferred term (PT) will be sorted by international order for SOC and by descending order of PT in the dapagliflozin treatment group.

No statistical tests to compare crude AE frequencies between treatment groups will be performed.

A summary table of the total number and percent of patients with SAE, DAE, AE leading to dose reduction and temporary interruption, and for each category of AE of interest per treatment group will be provided.

4.2.5.2 Serious adverse events

SAEs will be presented as described below both on treatment and on+off treatment.

The number and percent of patients with SAEs will be presented by SOC, PT and treatment group. The most common SAEs will also be presented by PT and treatment group only.

AEs with outcome death will be presented separately by SOC and PT.

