3.3 Safety variables

The safety and tolerability of dapagliflozin will be evaluated from serious adverse events (SAEs), adverse events leading discontinuation (DAEs) of study drug, changes in clinical/haematology parameter and adverse events (AEs) of interest (volume depletion, renal events, major hypoglycaemic events, fractures, diabetic ketoacidosis, AEs leading to amputation and AEs leading to a risk for lower limb amputations [“preceding events”]).

SAEs will be collected from time of informed consent until and including the patient’s last visit.

Non-serious AEs will be collected from randomization until and including the patient’s last visit, only if it is a DAE, an AE of interest, an AE leading to a potential endpoint or the AE is the reason for interruption of study drug or dose reduction.

Deaths and HF events will be recorded as SAEs in the database, but will not be reported to health authorities to avoid unnecessary unblinding of efficacy endpoints that are fulfilling the SAE criteria. If it is determined by the CEA committee that a potential endpoint does not meet the endpoint criteria, but is judged by investigators to fulfil the SAE criteria, then the event will be reported to AZ patient safety data entry site and if applicable to the health authorities.

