4.2.5.4 Adverse events of interest

Each category of AEs of interest will be presented separately. AEs of interest fall in the categories volume depletion, renal events, major hypoglycaemic events, fractures, diabetic ketoacidosis (DKA), AEs leading to amputation and AEs leading to a risk for lower limb amputations [“preceding events”].

In addition to the pre-specified events of interest, analysis and presentation of potential events of Fournier’s gangrene will also be included.

Potential DKA events will be adjudicated. The adjudicated outcome will be considered the main analysis for DKA.

For each AE of interest, a summary table including the number and percent of patients with any event in the AE category, SAE, DAE, AE leading to interruption and dose reduction. Each AE of interest category will also be tabulated with frequency by PT.

In addition to presentations of the number of patients with event, the total number of events counting multiple events per patient will be presented for AE of special interest, where relevant eg for major hypoglycaemic events and amputation.

In addition to the presentation of on-treatment events, on+off presentations will be provided for all AEs of interest.

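### The total of patients with any SAE mixes the primary efficacy outcome with other serious harm, and no overall SAE count without it is planned

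*SAP*

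**What the plan says.** Section 3.3 fixes what enters the SAE data: "Deaths and HF events will be recorded as SAEs in the database, but will not be reported to health authorities". Only the reporting to authorities is held back; the events themselves stay in the SAE counts. Section 3.1 makes CV death, HF hospitalization and urgent HF visits the primary endpoint, so the SAE data contain it.

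The overall count is set in section 4.2.5.1: "A summary table of the total number and percent of patients with SAE, DAE, AE leading to dose reduction and temporary interruption", per arm, together with each category of AE of interest. The same section limits the collection of non-serious AEs to selected categories and plans no general summary of all AEs.

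For detail, section 4.2.5.2 says "The number and percent of patients with SAEs will be presented by SOC, PT and treatment group" and "SAEs will be presented as described below both on treatment and on+off treatment". Neither section 4.2.5.1 nor 4.2.5.2 leaves endpoint events out of any overall SAE count.

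Other displays stand beside these. Section 4.2.5.2 adds "AEs with outcome death will be presented separately by SOC and PT". Section 4.2.5.3 tabulates AEs leading to discontinuation, interruption or dose reduction by SOC and PT. Section 4.2.5.4 states "Each category of AEs of interest will be presented separately". Section 4.2.5.1 also says "No statistical tests to compare crude AE frequencies between treatment groups will be performed".

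**The concern.** SAEs are the first outcome listed under the safety objective (section 1.1.3). Because all-AE summaries are not planned, the SAE total is the only overall, untargeted count of harm, apart from the counts of AEs that led to a change in study drug. If the drug does what the design assumes, fewer treated patients have an HF event or CV death, and the total drops for that reason alone. Equal totals in the two arms would then be compatible with more patients on dapagliflozin having some other serious event.

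The SOC/PT rows do not let a reader rebuild the number of patients with any SAE other than an endpoint event, because one patient can appear in several rows. What is at stake is an excess spread thinly over many unexpected terms, which no single row would show.

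**Working it through.** **Inputs from section 1.4.** Hazard ratio 0.80; one-sided alpha 2.5%; power 90%; 844 events; 1:1 allocation of 4500 patients (2250 per arm); 11% per year on placebo; average follow-up about 24 months. The SAP gives no SAE rate.

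**The plan's own figure.** Schoenfeld's formula, 4(1.960 + 1.282)² / (ln 0.80)², gives 845 events after rounding up, against 844 stated. Power with 844 events is 90.0%. The figure reproduces.

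**Endpoint risk at 24 months, 11% read as annual risk.**
- Placebo: p = 1 − 0.89² = 20.8%, or 468 patients.
- Dapagliflozin: d = 1 − 0.89^(2 × 0.80) = 17.0%, or 383 patients.
- The sum is 851, close to 844. The difference is 85 patients, or 3.8 points.

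**Offset in the total.** Let q be the placebo risk of any other SAE (assumed) and q₁ the risk on dapagliflozin. With independence, the any-SAE risk is 1 − (1 − endpoint risk)(1 − other-SAE risk). Setting the two arms equal gives q₁ = 1 − (1 − q)(1 − p)/(1 − d).

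If every endpoint event falls in the SAE table, (1 − p)/(1 − d) = 0.7921/0.8299 = 0.954. If only half of the endpoint hazard does, for example because the on-treatment window ends 30 days after the last dose, then p = 11.0%, d = 8.9% and the ratio is 0.977.

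| Assumed q | Share of endpoint hazard in table | q₁ | Offset excess (points) | Patients of 2250 | Any-SAE total, both arms |
|---|---|---|---|---|---|
| 20% | all | 23.6% | 3.6 | 82 | 36.6% |
| 30% | all | 33.2% | 3.2 | 72 | 44.6% |
| 40% | all | 42.7% | 2.7 | 61 | 52.5% |
| 20% | half | 21.8% | 1.8 | 41 | 28.8% |
| 30% | half | 31.6% | 1.6 | 36 | 37.7% |
| 40% | half | 41.4% | 1.4 | 31 | 46.6% |

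For q = 30% with all events counted, the difference of 33.2% v 30.0% has a nominal z of about 2.3, while both totals read 44.6%. With half counted, the nominal z is 1.2.

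**Sensitivity.** Reading 11% as a hazard of 0.11 per year gives 807 expected events, a worse fit to 844, and offsets of 3.4 to 2.6 points (all) or 1.7 to 1.3 points (half). If sicker patients tend to have both kinds of event, fewer patients enter the total only because of an endpoint event, and the offset shrinks.

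**The case against.** The strongest reply is that nothing here is misstated. The all-SAE counts follow the recording rule in section 3.3, no test or decision is tied to the total, and the harms the plan expects are displayed elsewhere. Each AE-of-interest category has its own table with an SAE count, and Fournier's gangrene is presented as well. All of this stands. It confines the problem to a diffuse excess of unexpected events. It does not remove the problem, because readers will compare the totals whether or not they are tested.

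A reader might infer that the SOC/PT tables also hide harm. They do not do so in the same way. HF terms have their own PT rows, SOC rows that hold no HF or fatal terms are essentially untouched by an HF benefit, and an excess in one specific term stays visible. The cancellation sits in the any-SAE total of section 4.2.5.1.

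Two objections to a remedy also stand. Section 3 counts deaths of undetermined cause as CV deaths in the primary analysis, so removing every primary event would take possibly drug-related deaths out of the safety count. And if the drug lowers mortality, treated patients have longer to experience other SAEs, so a crude percentage without endpoint events could be tilted against it.

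**Conclusion.** The point holds in a limited form. The planned total of patients with any SAE combines efficacy with other serious harm, and no planned overall summary separates them. At the planning figures, a true effect on the primary endpoint could offset an excess of other SAEs of about 1.4 to 3.6 percentage points (31 to 82 patients per arm of 2250). That range rests on an assumed placebo other-SAE risk of 20-40%, on independence, and on half to all of the endpoint hazard falling in the SAE window.

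A reader might go further and conclude that the SAE totals are wrong, or that the plan would leave serious harm unseen. The document supports neither. The totals are correct for what they count, and several planned tables show specific harms apart from HF events. Nor does the calculation predict an excess; it shows only what the total could fail to reveal. This is a cheap improvement in presentation, not an error in the analysis.

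**What to change.** Keep every planned all-SAE summary. Beside them, add one row to the overview in section 4.2.5.1 and one SOC/PT table to section 4.2.5.2, giving patients with SAEs other than HF events and deaths adjudicated as CV, for the on-treatment and on+off periods. Keep deaths of undetermined cause in this count. Give the new row per 100 patient-years as well as in percent, to allow for unequal time at risk.

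State in the text how AE records are matched to adjudicated outcomes, which the SAP does not describe, and whether HF events means all those recorded as SAEs or only the confirmed ones. If only confirmed events are removed, unconfirmed HF events stay in the count and part of the efficacy effect stays with them.

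The cost is one row and one table from data the trial already collects, plus that matching rule. The downside is a second, descriptive SAE figure that must be read together with the all-SAE total.

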4.2.5.3 Adverse events leading to discontinuation, interruption or dose reduction

The number and percent of patients will be presented by SOC and PT for AEs leading discontinuation, AEs leading to temporary interruption and dose reduction (separately for each of the three categories based action taken “Drug Permanently Discontinued”, “Drug Interrupted” and “Drug Reduced” respectively).

4.2.5.4 Adverse events of interest

Each category of AEs of interest will be presented separately. AEs of interest fall in the categories volume depletion, renal events, major hypoglycaemic events, fractures, diabetic ketoacidosis (DKA), AEs leading to amputation and AEs leading to a risk for lower limb amputations [“preceding events”].

In addition to the pre-specified events of interest, analysis and presentation of potential events of Fournier’s gangrene will also be included.

Potential DKA events will be adjudicated. The adjudicated outcome will be considered the main analysis for DKA.

For each AE of interest, a summary table including the number and percent of patients with any event in the AE category, SAE, DAE, AE leading to interruption and dose reduction. Each AE of interest category will also be tabulated with frequency by PT.

In addition to presentations of the number of patients with event, the total number of events counting multiple events per patient will be presented for AE of special interest, where relevant eg for major hypoglycaemic events and amputation.

In addition to the presentation of on-treatment events, on+off presentations will be provided for all AEs of interest.

4.2.5.5 Laboratory Evaluation

All summaries of clinical chemistry/haematology parameters will be based on samples analyzed at the central laboratory, and presented in SI units.

The result and the change from baseline of each clinical chemistry/haematology tests, including estimated GFR, will be summarized by treatment group at each scheduled visit using descriptive statistics, including n, mean, SD, median and quartiles.

4.2.5.6 Marked laboratory abnormalities

The number and percent of patients with a marked abnormality in clinical laboratory tests will be summarized over time by treatment group.

Laboratory abnormalities will be evaluated based on marked abnormality (MA) criteria. The list of MAs is provided in Appendix A (Section 8.1)

An on-treatment value will be considered an MA if either

- the on-treatment value is beyond an MA limit AND the baseline value is not beyond the same limit,
OR
- both the baseline and on-treatment value are beyond the same MA limit AND the on-treatment values is more extreme (farther from the limit) than was the baseline

Laboratory MAs occurring during the on-treatment period will be summarized by treatment group. The directions of changes (high or low) in MAs will be indicated in the tables. Additionally, for each patient with a MA for a parameter, all the patient's values of that parameter over the treatment period will be listed.

4.2.6 Analysis of exploratory objectives

The analysis of the exploratory variables will in the same fashion as the primary and secondary efficacy variables be based on the ITT principle, including data irrespective of whether the patient has discontinued study drug.

The time to event endpoints including

- MI
- stroke
- first occurrences of serum potassium falling above/below defined thresholds
- the wider composite reflecting worsening HF (CV death, hospitalization for HF, urgent HF visit or worsening HF symptoms/signs leading to initiation of new treatment or augmentation of existing oral treatment)

will be analysed with the same methods as the primary endpoint.

Change from baseline to each visit for HbA1c, body weight, blood pressure and EQ-5D will be analysed with a repeated measures method. The analysis of HbA1c will be limited to patients with T2D at baseline as defined in Section 4.1. All non-missing visit data will be used, including measurements after discontinuation of study drug. The model will include terms for treatment group, visit, visit*treatment group and baseline measurement as a covariate. The model will be used to derive a least squares estimate of the treatment difference with 95% confidence interval and corresponding two-sided p-value. The missing data will not be imputed.

The proportion of patients with no worsening NYHA classification will be analyzed by a logistic regression by visit with treatment group, baseline NYHA and T2D at randomization. The odds ratio between treatment groups and its 95% confidence interval and corresponding two-sided p-value will be presented.

The proportion of patients with new diagnosis of T2D in non-diabetic patients (as defined in Section 4.1) will be analyzed by a logistic regression with treatment group and baseline HbA1c. The odds ratio between treatment groups and its 95% confidence interval and corresponding two-sided p-value will be presented. In addition to analysing patients who are non-diabetic at baseline, the subgroup of pre-diabetic patients as defined in Section 4.1 will be analysed.

The proportion of patients with new diagnosis of AF in patients without history of AF at baseline will be analysed with logistic regression with treatment group and T2D at randomization.

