1.1.4 Explorative objectives

Exploratory Objective:	Outcome Measure :
To compare the effect of dapagliflozin versus placebo on an expanded composite outcome reflecting worsening of HF.	Time to the first occurrence of any of the components of the expanded composite worsening HF outcome: 4. CV death 5. Hospitalization for HF 6. An urgent HF visit 7. Documented evidence of worsening HF symptoms/signs leading to initiation of a new treatment for HF sustained for at least 4 weeks or augmentation of existing oral therapy for HF (eg, increase in dose of diuretic) sustained for at least 4 weeks.
To determine whether dapagliflozin compared with placebo will have effect on New York Heart Association (NYHA) class.	Change in NYHA class from baseline.
To determine whether dapagliflozin compared with placebo will reduce the incidence of diagnosis of AF in patients without history of AF at baseline.	Proportion of patients without history of AF at baseline with a new diagnosis of AF during the study.
To determine whether dapagliflozin compared with placebo will result in a reduction of the incidence of hyper – and hypokalaemia.	Time to the first occurrence of each of any of the following central lab levels of serum potassium: 
 • >6.0 mmol/L • >5.5 mmol/L • <3.5 mmol/L • <3.0 mmol/L
To determine whether dapagliflozin compared with placebo will affect the number of events of doubling of serum creatinine.	Number of events with doubling of serum creatinine (compared with the most recent laboratory measurement).
To determine whether dapagliflozin compared with placebo will reduce the incidence of diagnosis of T2D in patients without diabetes at baseline.	Proportion of patients without T2D at baseline with a new diagnosis of T2D during the study.
To determine whether dapagliflozin compared with placebo will have effect on HbA1c in T2D subgroup.	Changes in HbA1c from baseline.

To determine whether dapagliflozin compared with placebo will have an effect on systolic BP.	Change in systolic BP from baseline.
To determine whether dapagliflozin compared with placebo will have an effect on body weight.	Change in body weight from baseline.
To determine whether dapagliflozin compared with placebo will reduce the incidence of myocardial infarction (MI).	Time to first fatal or non-fatal MI.

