3.1 Primary variable

The primary efficacy variable is time from randomization to the first occurrence of any event in the composite of CV Death, hospitalization for HF or an urgent HF visit.

The three components of the endpoint will be individually adjudicated by the CEA committee.

Patients who did not have an endpoint event will be censored at the earliest of date of WoC or non-CV death when applicable, and otherwise at the earliest of date of last clinical event assessment or PACD. Last clinical event assessment is defined as the last date when the event assessment question for a potential heart failure event was completed on the eCRF event assessment page. It is expected that patients alive and under study follow-up will have a clinical event assessment at their SCV after PACD

In analysis of hospitalization for HF and urgent HF visit to examine the contribution of each component of the composite endpoint, date of death from any cause will be an additional point of censoring.

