All components of the composite endpoint will be defined and described in detail in the CEA charter. The components sustained eGFR decline of $\geq 50\%$ from baseline and sustained eGFR < 15 ml/min/1.73m² will however not be adjudicated by the CEA.

Sustained eGFR decline of $\geq 50\%$ from baseline and sustained eGFR < 15 ml/min/1.73m² will be based on two consecutive central laboratory values at least 28 days apart below the respective limit. The start date of the event is the date of the first of the two qualifying consecutive central laboratory values. Thus, the analysis will include eGFR events with onset prior to PACD that are confirmed after PACD, in addition to those eGFR events confirmed prior to PACD.

Chronic dialysis will be adjudicated as treatment ongoing for at least 28 days, or when the ESRD is deemed irreversible and the dialysis treatment was stopped before day 28. Similar to the eGFR events, the onset date of chronic dialysis will be the date when the qualifying dialysis treatment started. Chronic dialysis, renal transplant and renal death will be independently adjudicated as defined in the CEA charter. Deaths adjudicated with ‘undetermined’ cause will not be considered as renal death.

Patients who do not have an endpoint event will be censored at the earliest of date of WoC and non-renal death when applicable, and otherwise at the earliest of date of last clinical event assessment and PACD. Clinical event assessment will be captured by the question for potential renal events on the eCRF event assessment page. The earliest assessment date among components will be used as the censoring date. For example, for the last clinical event assessment, if the central laboratory eGFR assessment is not done in conjunction with the assessment of dialysis and renal transplant, the date of last available central laboratory eGFR measurement will be used as the censoring date.

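### Time to hyper- or hypokalaemia borrows the primary-endpoint method, which sets no baseline at-risk rule for potassium and censors on the heart-failure question instead of the last potassium sample

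*SAP*

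**What the plan says.** Section 1.1.4 asks whether dapagliflozin "will result in a reduction of the incidence of hyper – and hypokalaemia". The outcome measure is "Time to the first occurrence of each of any of the following central lab levels of serum potassium", with limits of >6.0, >5.5, <3.5 and <3.0 mmol/L.

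Section 4.2.6 includes "first occurrences of serum potassium falling above/below defined thresholds" in a short list of time-to-event endpoints and says that these "will be analysed with the same methods as the primary endpoint". It adds nothing specific to potassium.

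The primary method is set out in three places:

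- Sections 2.1.1 and 4.2.3: the full analysis set (FAS), meaning all randomized patients. Section 2.1.1 also makes the FAS the primary set for exploratory efficacy variables.
- Section 4.2.3: event-free patients are censored using withdrawal of consent, non-CV death, last clinical event assessment and the primary analysis censoring date (PACD).
- Section 3.1: "Last clinical event assessment is defined as the last date when the event assessment question for a potential heart failure event was completed". This is a case report form entry, not a laboratory date.

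The introduction to Section 3 says that censoring is described for each respective endpoint. No such description exists for potassium.

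**The concern.** The primary method was written for clinical events that a site visit or call can establish and that a patient cannot already have at randomization. A central-laboratory threshold has neither property.

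**At-risk set.** Nothing removes a patient already beyond the limit, and nothing requires a change from baseline. Someone with potassium 3.3 mmol/L at baseline and 3.3 at the next sample is a first occurrence of <3.5, although the objective is worded as incidence.

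**Censoring.** A completed heart-failure question does not show that blood was drawn. Section 1.2.3 allows modified follow-up after study drug is stopped, and Section 4.2.6 keeps those patients in the analysis. If the question continues to be answered without sampling, that time is at risk and event-free although no central-laboratory event could be seen.

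**Death.** The primary rule names only non-CV death as a censoring event, because CV death is itself a primary event. CV death is not a potassium event, and the borrowed rule does not mention it.

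At stake are four sets of exploratory hazard ratios and event rates that would be read as incidence while mixing prevalent with new cases, over time that may be partly unobserved.

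**Working it through.** **1. How the SAP treats comparable cases**

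| Analysis | Abnormal at baseline | End of observation |
|---|---|---|
| Renal composite (3.2.4) | eGFR decline measured from baseline | If eGFR was not taken with the other assessments, "the date of last available central laboratory eGFR measurement will be used as the censoring date" |
| HF hospitalization and urgent HF visit as components (3.1) | not applicable | Death from any cause added as a censoring point |
| Marked abnormalities (4.2.5.6) | Counts if "the on-treatment value is beyond an MA limit AND the baseline value is not beyond the same limit", or if both are beyond it and the later value is more extreme | On-treatment period |
| New AF, new T2D (4.2.6) | Only patients without the condition at baseline | not applicable |
| Potassium thresholds (4.2.6) | No rule | Primary rule: last heart-failure question |

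The SAP therefore already contains each element the potassium analysis lacks. The marked-abnormality table does not fill the gap: its potassium limits in Appendix A are ≤2.5 and ≥6.0 mmol/L, so >5.5, <3.5 and <3.0 have no baseline-referenced threshold analysis.

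**2. Size of the baseline effect**

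The SAP states no potassium figure, so there is nothing to reproduce. All inputs below are assumptions:

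- p, share beyond the limit at baseline: 0.02 or 0.05
- r, share of those who are beyond it again after baseline: 0.3 or 0.5, the same in both arms
- i, placebo risk of newly crossing the limit: 0.03, 0.08 or 0.12
- true hazard ratio among patients within the limit at baseline: 0.80

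Formulas:

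- placebo risk P = p·r + (1−p)·i
- treated risk T = p·r + (1−p)·[1 − (1−i)^0.8]
- carried-over share of placebo events = p·r / P
- apparent hazard ratio = ln(1−T) / ln(1−P)

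Mildest case (p=0.02, r=0.3, i=0.12): P = 0.006 + 0.98×0.12 = 0.1236; T = 0.006 + 0.98×0.0972 = 0.1013. Share 0.006/0.1236 = 4.9%; apparent hazard ratio 0.809.

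Most extreme case (p=0.05, r=0.5, i=0.03): P = 0.025 + 0.95×0.03 = 0.0535; T = 0.025 + 0.95×0.0241 = 0.0479. Share 0.025/0.0535 = 46.7%; apparent hazard ratio 0.892.

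The extreme case needs more patients beyond the limit at baseline (5%) than newly crossing it (3%). Pairing rarer with rarer (p=0.02 with i=0.03; p=0.05 with i=0.12) gives shares of about 12% to 25% and apparent hazard ratios of about 0.82 to 0.85.

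**3. Dependence on the persistence assumption**

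Let persistence in the extreme case also fall by 20% on treatment, from 0.5 to 0.4. Then T = 0.02 + 0.95×0.0241 = 0.0429, and the apparent hazard ratio is ln(1−0.0429)/ln(1−0.0535) = 0.797. The attenuation disappears.

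**4. Unsampled follow-up**

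If a share u of follow-up is unsampled but counted, the observed rate is roughly (1−u) times the true rate. The observed ratio is then 0.80 × (1−u_dapagliflozin)/(1−u_placebo). The shares are assumptions.

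- Equal shares (5%, 10% or 20% in both arms): rates are 5%, 10% or 20% too low; the ratio stays at 0.80.
- 15% on placebo, 10% on dapagliflozin: 0.80 × 0.90/0.85 = 0.85.
- 10% on placebo, 15% on dapagliflozin: 0.80 × 0.85/0.90 = 0.76.

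**The case against.** **Same methods may mean only the Cox model.** Section 4.2.4 analyses the time-to-event secondary endpoints in the same manner as the primary variable, yet refers to endpoint-specific censoring. Potassium could be meant likewise. This is fair as a guess at intent, but Section 4.2.3 makes the censoring dates part of the primary method and no other rule is given for potassium. The gap stands on either reading.

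**Analysing all randomized patients is legitimate.** Randomization balances baseline cases and the test under no effect remains valid. That is correct. Restricting the at-risk set is a choice of what to estimate. The case for it is that the objective says incidence and that the SAP restricts new AF and new T2D in this way.

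**The marked-abnormality rule is not an exclusion.** It also counts worsening from an abnormal baseline. This stands: it is a precedent for referring to baseline, not for dropping patients.

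**Missed samples are conjecture.** Section 1.2.3 prefers that patients who stop study drug keep to planned visits and does not say that modified follow-up omits blood tests. This stands too. Section 3.2.4 shows that the SAP foresees a laboratory value missing at an assessment, but nothing indicates how often.

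**Stronger readings not supported.** A reader might infer that every patient beyond the limit at baseline becomes an event. One whose later values are all within the limit does not. A reader might also infer that dilution toward 1 is certain, or is worst for the rarer limits. The first requires that treatment leaves persistence unchanged; the second holds only if baseline prevalence stays fixed while incidence falls. The documents establish neither.

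**Conclusion.** The point holds as a mismatch between a laboratory endpoint and a borrowed method. Taken literally, Section 4.2.6 counts unchanged baseline abnormalities that recur after baseline as first occurrences, treats follow-up after the last potassium sample as event-free, and leaves CV death out of the censoring events.

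Its size cannot be obtained from the documents. The 0.81 to 0.89 range for a true 0.80 rests wholly on assumed prevalence, persistence and incidence, and on no treatment effect on persistence. Unsampled time distorts the ratio only if the arms differ, and its extent is unknown.

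The consequence is limited. These endpoints are outside the testing hierarchy and Section 4.1 treats their p-values as nominal, so no confirmatory conclusion changes. Section 4.2.5.5 also gives change from baseline by visit for the clinical chemistry tests. This is a cheap improvement of minor priority.

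**What to change.** Add to Section 4.2.6:

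> For each potassium threshold, the analysis includes patients whose baseline central-laboratory potassium is not beyond that threshold, and counts post-baseline samples only. Event-free patients are censored at the earliest of the last central-laboratory potassium measurement, death from any cause, WoC and PACD.

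Baseline can follow the laboratory definition already in Section 4.1. Stratification and covariates stay as planned. The programming specification should say how patients with no baseline or no post-baseline potassium are handled. The all-FAS analysis may be kept as supportive.

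The cost is two sentences and a small programming change, using data already collected and best settled before unblinding. The analysis set becomes slightly smaller for each threshold. Patients who worsen from an already abnormal baseline, for example from 5.6 to 5.9 mmol/L against the >5.5 limit, are not counted in the main analysis; the supportive all-FAS analysis would still show them.
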